### Appendix IV: Therapeutic efficacy adjustments and safety monitoring

#### Advanced Pump Thrombosis Monitoring Protocol

- Monitor LDH at baseline and after initiation of determined antithrombotic therapy based on randomization algorithm once a week during first 4 weeks, then once every 2 weeks for the next month and monthly after that
- If LDH rises more than 1.2x baseline:
  - repeat LDH within the next 1-3 business days
  - monitor plasma free hemoglobin (pf-Hb) and haptoglobin if available; and total bilirubin
  - o complete evaluation with the team to rule out other reasons for LDH rise
  - o echocardiogram to evaluate for aortic insufficiency
  - o prompt study team to review within 48 hours
  - retrospective data log files analysis (particularly rotor noise and rotor displacement trends) followed by prospective analysis 2 weeks post event

#### Appendix V: Apixaban effect reversal protocol

In case of need of reversal of the effect of apixaban, following protocol will be executed.

## DOT HM3 Study – Statistical analysis plan

Stable HM3 patients who have not suffered a Major hemocompatibility-related adverse after index hospitalization discharge and are at least 3 months post-implant will be screened for participation in the study. Upon meeting the study criteria and patient informed consent, the individuals will be randomized to either continued therapy with a Vitamin K antagonist and aspirin or conversion to apixaban 5 mg twice a day in a 1:2 manner; the apixaban group will be stratified further by 1:1 randomization to continued use of 100 mg aspirin once daily or cessation. Thus, 45 patients are planned to be enrolled and randomized in 3 subgroups of 15 patients in each arm. The sample size of 45 patients was calculated to be sufficient to elucidate any safety signal. After 180 days follow-up is reached, the Vitamin K antagonist and aspirin arm will be transitioned to apixaban and randomized in a 1:1 manner to groups with or without aspirin.

Survival free of a hemocompatibility-related adverse events event (Stroke ischemic/hemorrhagic, Pump thrombosis, Severe bleeding, Peripheral arterial thromboembolic events) at the endpoint of 90 days will be evaluated as primary endpoint as proportion of success calculated between the apixaban and the warfarin arms. The prevalence (percent of patients with events) and incidence (event rates in events per pt-year) of adverse events and rehospitalizations will be determined. The secondary endpoints include an evaluation of the following adverse events per INTERMACS definitions (version 5.0) throughout the study period:

- Stroke (ischemic/hemorrhagic)
- Pump thrombosis
- · Major bleeding
- GI Bleeding
- Peripheral arterial thromboembolic events
- Transient ischemic attack
- Hemolysis
- Venous thromboembolism
- Myocardial infarction
- Right heart failure
- Cardiac arrhythmias
- Liver and kidney dysfunction
- Death due to any cause

Time to event analyses will be done by Kaplan-Meier analysis. The overall outcomes being evaluated for clinical safety as assessed by the study's oversight committee.

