### 1 INTRODUCTION

HeartMate 3 (HM3) Left Ventricular Assist System (LVAS) is a centrifugal, fully magnetically levitated, continuous-flow pump designed to facilitate hemocompatibility by reducing shear stress on blood elements and to optimize pump washout by intrinsic pulsatility.

The Multicenter Study of MagLev Technology in Patients Undergoing Mechanical Circulatory Support Therapy with HeartMate 3 (MOMENTUM 3) trial 2-year data demonstrated an absence of confirmed pump thrombosis requiring pump exchange and marked reduction in stroke rates. On the backdrop of conventional anticoagulation protocols used in the study, observed bleeding complication rates in HM 3 were reduced, yet there is a need for further improvement as the overall intensity of conventional anti-thrombotic therapy represents a major contributor to non-surgical bleeding-related outcomes.

The HM3 LVAS Instructions for Use (IFU) recommend maintaining patients on Warfarin and Aspirin for long-term anticoagulation therapy. Recent results of The Minimal AnticoaGulation EvaluatioN To aUgment heMocompatibility (MAGENTUM 1) pilot study has demonstrated substantially lower-intensity anticoagulation (INR range 1.5 - 1.9) is achievable and supports the safety of lower targets with select patients implanted with the HeartMate 3 beyond 1 year with no thromboembolic complications or pump thrombosis. The observed outcomes were similar to those with the higher intensity anticoagulation targets and further support a signal of enhanced intrinsic thromboresistance of the HM3.

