### 2 STUDY OBJECTIVES

#### 2.1 PRIMARY ENDPOINT

The primary endpoint to evaluate the safety and feasibility of apixaban with the HeartMate 3 LVAS is survival free of major HRAEs (hemocompatibility related adverse events) at 90 days post-enrollment. The primary analysis will compare the apixaban groups (n=30) to control (n=15). A separate analysis will compare the primary endpoint in patients randomized to receive aspirin (n=15) and no-aspirin (n=15) within the apixaban group.

Major HRAEs include:

- Stroke (ischemic/hemorrhagic)
- Pump thrombosis
- Severe bleeding (see Appendix II)
- Peripheral arterial thromboembolic events

HRAEs are influenced by several patient-specific risk factors, including anticoagulation, poor general health, altered circulation, the pump's hemocompatibility, and the presence of other comorbidities (e.g., AF, infections, etc.). In standard use, clinicians balance the risk of stroke and other thromboembolic (TE) events with the increased risk of bleeding when prescribing

anticoagulation or antiplatelet medications. Therefore, a composite endpoint comprising TE, bleeding, and pump-related events were chosen for the analysis.

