### 3.3.2 Adverse events adjudication and outcomes assessment

All suspected or confirmed HRAEs (safety surveillance see Appendix IV) will be promptly reported to and adjudicated by the Expert Advisory Committee to determine individual patient safety to continue with the assigned treatment arm and the overall study safety and eligibility for continuation. All adverse events will be periodically reported to the Institutional Ethics Committee.

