#### Appendix I: Study design flow chart

### Appendix II: Severe Bleeding Definition

#### SEVERE BLEEDING:

Type A: (Meets any of the below)

- Overt bleeding plus hemoglobin drop of 3 to < 5 g/dL(30-50g/L) (provided hemoglobin drop is related to bleed)
- Any transfusion with overt bleeding

Type B: (Meets any of the below)

- Overt bleeding plus hemoglobin drop 5 g/dL (50g/L) or greater (provided hemoglobin drop is related to bleed)
- Cardiac tamponade
- Bleeding requiring surgical intervention for control (excluding dental, nasal, skin, or hemorrhoid)
- Hypotension attributable to bleeding and requiring intravenous vasoactive agents for hemodynamic support
- Intracranial Hemorrhage that does not meet the definition of hemorrhagic stroke

Type C1: Probable fatal bleeding; no autopsy or imaging confirmation but clinically suspicious

Type C2: Definite fatal bleeding; overt bleeding or autopsy or imaging confirmation

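### The SAP says 45 patients were calculated to reveal any safety signal, but gives no calculation; at an assumed 90-day risk of 5%, 30 apixaban patients would show no case 21% of the time, and at 2%, 55%

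*SAP*

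**What the plan says.** The first paragraph of the SAP describes three groups of 15 and then states: "The sample size of 45 patients was calculated to be sufficient to elucidate any safety signal". Nothing else in either document says what the sample can show. Protocol section 3.1 only anticipates 45 patients, section 3.3.1 splits them into three groups of 15, and section 5.3 (data analysis) has no sample-size text.

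Protocol section 2.1 sets two comparisons: "The primary analysis will compare the apixaban groups (n=30) to control (n=15"), and a separate one of "patients randomized to receive aspirin (n=15) and no-aspirin (n=15) within the apixaban group". The SAP gives the primary measure as the "proportion of success calculated between the apixaban and the warfarin arms". It names no test and no confidence interval for it. It adds Kaplan-Meier analysis, also without confidence limits.

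**The concern.** The sentence makes two claims: that a calculation was done, and that its result covers every safety signal. The first cannot be verified. The second cannot be true of 30 patients followed for 90 days, because an uncommon event can easily fail to appear.

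Uncommon events are relevant here. The primary endpoint includes stroke, pump thrombosis and peripheral arterial thromboembolism. The Protocol's introduction reports, for this pump on conventional anticoagulation, "an absence of confirmed pump thrombosis requiring pump exchange and marked reduction in stroke rates", and for a low-intensity warfarin pilot in selected patients, "no thromboembolic complications or pump thrombosis". These passages give no rates, but they point to low background risks for the thrombotic components.

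The Expert Advisory Committee is to judge "the overall study safety and eligibility for continuation" (Protocol section 3.3.2), and the SAP leaves the overall safety assessment to the oversight committee. With this sentence in place and no interval planned, neither the committees nor later readers are told how large a risk the data could miss.

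**Working it through.** **Inputs.** From the documents: 45 patients, 30 apixaban and 15 control; apixaban split 15 and 15; primary endpoint at 90 days. Not in the documents: event risks, effect, margin, significance level, sidedness, power, test, dropout. The risks of 2%, 5% and 10% and the tripled risk below are assumptions.

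**1. The plan's own figure.** Only the sum 3 × 15 = 45 can be reproduced.

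**2. Chance of seeing no case.** If each of *n* patients has risk *p* and all are followed to day 90, the chance of zero cases is (1 − p)^n. No test is involved.

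| Assumed 90-day risk | n = 30 | n = 15 |
|---|---|---|
| 2% | 0.98^30 = 55% | 0.98^15 = 74% |
| 5% | 0.95^30 = 21% | 0.95^15 = 46% |
| 10% | 0.90^30 = 4% | 0.90^15 = 21% |

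The risk that has an 80% chance of showing at least one case is 1 − 0.2^(1/n): 5.2% for n = 30 and 10.2% for n = 15.

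**3. What zero events would exclude.** The exact (Clopper-Pearson) two-sided 95% upper limit after zero events is 1 − 0.025^(1/n): 11.6% for 0/30 and 21.8% for 0/15.

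**4. Reading the claim as a difference between arms.** Because no test is stated, four were tried at level 0.05, with power found by enumerating all 31 × 16 possible outcomes and apixaban assumed to triple the control risk.

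| Test | 10% v 30% | 15% v 45% | Control risk at which power is 80% |
|---|---|---|---|
| Fisher, two-sided | 25% | 46% | 22.9% |
| Fisher, one-sided | 34% | 54.5% | 21.5% |
| Chi-square, uncorrected, two-sided | 34% | 54.5% | 21.5% |
| Chi-square, uncorrected, one-sided | 44% | 67% | 18.1% |

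A control risk near 20% cannot be ruled out for the composite, because Appendix II of the Protocol counts "Any transfusion with overt bleeding" as severe bleeding. This step therefore does not show that the sample is too small for the comparison. It shows only that sufficiency depends on inputs the plan does not give.

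**5. Precision that intervals would show.** Take an invented result of 28/30 event-free on apixaban and 14/15 on control. The exact 95% intervals are 77.9% to 99.2% and 68.1% to 99.8%. The event proportions are equal (2/30 = 1/15 = 6.7%), yet the Newcombe 95% interval for the risk difference, apixaban minus control, runs from −24 to +16 percentage points.

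**The case against.** **This is a feasibility trial and needs no power calculation.** That is fair as to the size. The Protocol describes the trial as one of feasibility and safety, and nothing here shows that 45 is the wrong number. But the SAP does not describe 45 as a feasibility size; it says the number was calculated to be enough.

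**The 2% and 5% risks are not the trial's, and bleeding may be far more common.** True. They suit single thrombotic components rather than the composite, and the introduction's evidence is indirect: one statement is limited to thrombosis requiring exchange, and a marked reduction in stroke gives no level. But a claim about any signal has to hold for uncommon events too.

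**Follow-up does not stop at day 90.** Secondary adverse events are evaluated throughout the study, and uneventful patients continue to day 180. If the hazard is constant and all 30 patients reach day 180, the chance of no case becomes 0.95^60 = 4.6% at a 5% 90-day risk and 0.98^60 = 30% at 2%. Control patients who move to apixaban after day 180 would add exposure. This weakens the 5% figure outside the primary window. It does not rescue *any*, and the formula in step 2 applies to the risk over whichever window is used.

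**Nothing depends on the sentence.** No decision rule uses it, neither document says that a null result will be read as safety, and suspected events are reported promptly and adjudicated one by one. This limits the harm, but the plan's only statement of its capability remains wrong.

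**Conclusion.** The concern holds. The reported calculation has no stated inputs, and the claim to reveal any safety signal is false as written. In the 90-day primary window, 30 apixaban patients would show no case of an event 21% of the time at a 5% risk and 55% of the time at a 2% risk; for a single 15-patient arm the figures are 46% and 74%. These rest on assumed risks and complete follow-up; earlier losses would raise the chance of seeing nothing. The sample will very probably show an event with a 10% risk (96% for 30 patients). For the comparison between arms the conclusion is only that sufficiency is not demonstrated. This should be fixed, but it does not call the number of patients into question.

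**What to change.** If a calculation exists, put its inputs in the SAP: event rates, effect or margin, level, power, test, and the signal it covers. If not, remove the claims that the size was calculated and that it covers any signal, and replace the sentence with text such as:

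> Forty-five patients (30 apixaban, 15 control) is a feasibility size. If no event occurs in 30 patients, the exact two-sided 95% upper limit for its risk is 11.6% (21.8% for 15 patients). An event with a 90-day risk of 5.2% has an 80% chance of being seen at least once in 30 patients (10.2% for 15).

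Also plan an exact 95% interval for the event-free proportion in each arm, and a 95% interval for the difference by a method named in advance, for example Newcombe. These need a fixed denominator, so the SAP should say how patients transplanted, explanted or withdrawn before day 90 are counted; confidence limits on the planned Kaplan-Meier estimates would help with such losses. A sentence saying that the lack of an observed difference is not in itself evidence of safety is optional but useful.

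The cost is a few lines of SAP text and a few more numbers in tables already planned. The stated claim becomes more modest and the intervals will be visibly wide.

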### 3.2 STUDY DURATION

Patients enrolled will be followed-up for 90 days post-transition to a designated antithrombotic regimen based on randomization. Provided the individual patients clinical course is uneventful regarding the primary endpoint, the patient's follow-up within the antithrombotic study protocol will be extended to the next pre-specified time point for analysis at 180 days. After the 180 days timepoint is reached, the patients will be given a chance to prolong the study until 1 year. All apixaban subsets will be treated according to their original study arm, the patients from the Vitamin K antagonist and aspirin group will be randomized in a 1:1 manner to apixaban with or without aspirin.

If the individual uneventful primary safety endpoint is established, the patient follow-up will be prolonged with next pre-specified time point for analysis at 1 year. If the second safety endpoint is reached, the patients could be followed for the duration of support with the HeartMate 3.

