#### 5.2.8 Outcome

The patient's outcome (transplanted, expired, explanted or withdrew) and date of outcome will be captured.

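### If Kaplan-Meier is applied to the individual non-fatal adverse events, one minus Kaplan-Meier overstates their cumulative risk, because death, transplant and explant can enter only as censoring

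*SAP*

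**What the plan says.** The SAP covers time-to-event analysis in one sentence: "Time to event analyses will be done by Kaplan-Meier analysis". It attaches no endpoint list, censoring rule or competing-risk method. Protocol section 5.3 names no time-to-event method at all.

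The sentence comes directly after the secondary endpoints, which the SAP introduces with "The secondary endpoints include an evaluation of the following adverse events per INTERMACS definitions (version 5.0) throughout the study period". Of the 13 items listed, 12 are event types other than death from any cause. Protocol section 3.2 sets analysis points at 180 days and 1 year, and adds that "the patients could be followed for the duration of support with the HeartMate 3".

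Protocol section 5.2.8 says the patient's "outcome (transplanted, expired, explanted or withdrew) and date of outcome will be captured". Neither document gives these outcomes a role in the analysis.

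Two other parts of the plan limit the point. The primary endpoint is "survival free of major HRAEs (hemocompatibility related adverse events) at 90 days post-enrollment", and the SAP says it "will be evaluated as primary endpoint as proportion of success calculated between the apixaban and the warfarin arms". For adverse events generally, the SAP also states: "The prevalence (percent of patients with events) and incidence (event rates in events per pt-year) of adverse events and rehospitalizations will be determined".

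**The concern.** A Kaplan-Meier curve for one non-fatal event has two states, event-free and event. A patient who dies, or who leaves device support by transplant or explant, fits neither and has to be censored. Censoring assumes that this patient still carries the same future risk as those who remain. After death that is false for every event, and after removal of the pump it is false for pump thrombosis. One minus Kaplan-Meier then describes a setting in which nobody dies or is transplanted. It exceeds the proportion who actually have the event whenever a terminal outcome precedes a later event.

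The gap widens with time, so it matters most for curves carried to 180 days, 1 year or beyond. At stake are the absolute risks reported for each regimen. If terminal outcomes are unequal between groups, a small part of any difference between their curves is at stake too.

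**Working it through.** **Plan's own figure.** There is none to reproduce. The documents state no event risk, death rate, transplant rate or Kaplan-Meier estimate.

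**Inputs from the documents.** Horizons are 90 days, 180 days and 1 year (Protocol section 3.2). Group sizes are 30 on apixaban, split 15 and 15 by aspirin, and 15 on control (Protocol section 2.1).

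**Assumed inputs.** Constant hazards per patient-year: event of interest λ = 0.3; death plus transplant μ = 0.2, 0.4 or 0.6. These μ correspond to 1-year risks of 1 − exp(−μ) = 18%, 33% and 45%.

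**Formulas**, with t in years (days / 365.25):
- One minus Kaplan-Meier, terminal outcomes censored: 1 − exp(−λt)
- Cumulative incidence: [λ/(λ+μ)] × [1 − exp(−(λ+μ)t)]

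Example at 1 year with μ = 0.6: 1 − exp(−0.3) = 25.9%; (0.3/0.9) × [1 − exp(−0.9)] = 19.8%; excess 6.1 points, ratio 1.31.

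| Horizon | 1 − KM | Cumulative incidence, μ = 0.2 to 0.6 | Excess (points) | Binomial SE at the 1 − KM value, n = 30 / n = 15 |
|---|---|---|---|---|
| 90 days | 7.1% | 7.0% to 6.6% | 0.2 to 0.5 | 4.7 / 6.6 |
| 180 days | 13.7% | 13.1% to 11.9% | 0.6 to 1.8 | 6.3 / 8.9 |
| 1 year | 25.9% | 23.6% to 19.8% | 2.3 to 6.1 | 8.0 / 11.3 |

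The standard error is √[p(1−p)/n]. It ignores loss of follow-up, so the true sampling error is larger.

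**Wider range.** With 1-year event risks of 10% to 40% and 1-year terminal risks of 5% to 40%, again assumed, the excess is 0.02 to 0.70 points at 90 days, 0.06 to 2.48 at 180 days and 0.25 to 8.0 at 1 year. The 8.0-point case has a 40% event risk, where the standard error is √(0.4 × 0.6/30) = 8.9 points for n = 30.

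**Exact small-sample check.** Take 15 patients, two terminal outcomes followed by two events, and nobody else lost. Kaplan-Meier gives 1 − (12/13)(11/12) = 15.4%. Aalen-Johansen gives 2/15 = 13.3%, the proportion observed. If the two events come first, both give 13.3%. With 30 patients and the terminal outcomes first, the figures are 7.1% and 6.7%.

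**Largest distortion of the warfarin comparison.** Suppose, within the main assumptions, that one arm had no terminal outcomes and the other had μ = 0.6. The two biases would then differ by 1.8 points at 180 days. After that the control arm moves to apixaban (Protocol section 3.3.1 and SAP).

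**The case against.** The strongest reply is that the bias rests on an implementation the SAP does not state. The sentence may refer only to survival and to the survival-free composite, where death is a failure and Kaplan-Meier raises no competing-death problem. This stands in part: the bias is conditional. But the sentence carries no such limit and follows a list of 12 non-death event types, so the conditional reading is a natural one.

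Three stronger readings are tempting, and the documents do not support them.

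- *The reported adverse-event risks are biased.* The adverse-event summaries explicitly planned are the percent of patients with events, which lacks this bias, and events per patient-year, which is not a cumulative risk. The crude percent is still no full substitute at later times, because follow-up lengths will differ between patients.
- *The primary result is affected.* It is a 90-day proportion of a composite that includes survival, so death counts as a failure. How transplant or explant before day 90 is counted is not stated, but that is a separate gap.
- *The warfarin comparison is distorted at 1 year.* No randomized warfarin group remains after day 180. What remains is the aspirin versus no-aspirin contrast among patients first randomized to apixaban, and the single-group risks.

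It is also fair to say that stroke, bleeding, myocardial infarction and several other listed events can still occur after transplant or explant. For these, treating transplant as a competing event follows from choosing risk on device support in the presence of terminal outcomes as the target. Censoring at transplant answers a different question that someone might legitimately ask. The SAP should say which is meant. Death needs a rule under either.

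Finally, the top assumed rate, 0.6 per patient-year, is high for patients required to be stable, ambulatory and discharged home. Nothing in the documents supports or excludes it.

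**Conclusion.** The point holds in conditional form and is minor. If Kaplan-Meier is applied to individual non-fatal adverse events, the direction of the error is certain whenever a terminal outcome precedes a later event, and the error grows with follow-up. Its size rests wholly on assumed constant hazards. On those it is negligible at 90 days, small at 180 days, and between small and material at 1 year, where the ratio runs from 1.10 to 1.31. At every horizon it is smaller than one standard error for these group sizes. The case for acting is that a method without this bias costs almost nothing, not that any conclusion of the trial is shown to be at risk.

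**What to change.** Replace the single SAP sentence with wording that does three things:

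1. Names the endpoints that receive a time-to-event analysis, keeping Kaplan-Meier for all-cause death and for the death-inclusive composite.
2. For each non-fatal adverse event, defines the target as risk while on HeartMate 3 support in the presence of death, transplant and explant.
3. Reports the Aalen-Johansen cumulative incidence for those events, with death, transplant and explant as competing events and withdrawal as censoring.

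The type and date of outcome are already to be collected under Protocol section 5.2.8. The outcome field in the Appendix III spreadsheet omits withdrawal, so that category should be added to match. No extra patients or visits are needed.

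The costs are a little more analysis work and the need to commit to the estimand in writing. If no terminal outcome precedes an event, the two estimators agree and nothing is lost.

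The change does not repair the late follow-up itself. Under Protocol section 3.2, extension past 90 days depends on having had no primary event, and extension to 1 year is optional. Both can distort 180-day and 1-year risks under either estimator and need their own handling.
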